7.1.3 Laboratory Procedures/Assessments

Details regarding specific laboratory procedures/assessments for hematology, chemistry, urinalysis, and others are specified in Table 5. The Schedule of Assessments - Section 6.0 summarizes the laboratory procedures to be performed at each visit.

Laboratory tests for screening or entry into the Retreatment Phase should be performed within 10 days prior to the first dose of treatment. After Cycle -2, pre-dose laboratory procedures can be conducted up to 72 hours prior to dosing. Results must be reviewed by the investigator or qualified designee and found to be acceptable prior to each dose of trial treatment.

Table 5: Laboratory Tests

Hematology	Chemistry	Urinalysis	Other
Hematocrit	Albumin	Blood	Serum β -human chorionic gonadotropin†
Hemoglobin	Alkaline phosphatase	Glucose	(β -hCG)†
Platelet count	Alanine aminotransferase (ALT)	Protein	PT (INR)
WBC (total and differential)	Aspartate aminotransferase (AST)	Specific gravity	aPTT
Red Blood Cell Count	Lactate dehydrogenase (LDH)	Microscopic exam (If abnormal)	Total triiodothyronine (T3)
Absolute Neutrophil Count	Carbon Dioxide ‡	results are noted	Free tyroxine (T4)
Absolute Lymphocyte Count	(CO_2 or bicarbonate)	Urine pregnancy test †	Thyroid stimulating hormone (TSH)
	Uric Acid		Blood for correlative studies
	Calcium		
	Chloride		
	Glucose		
	Phosphorus		
	Potassium		
	Sodium		
	Magnesium		
	Total Bilirubin		
	Direct Bilirubin (If total bilirubin is elevated above the upper limit of normal)		
	Total protein		
	Blood Urea Nitrogen		

† Perform on women of childbearing potential only. If urine pregnancy results cannot be confirmed as negative, a serum pregnancy test will be required.

‡ If considered standard of care in your region.

7.1.4 Other Procedures

7.1.4.1 Withdrawal/Discontinuation

When a subject discontinues/withdraws prior to trial completion, all applicable activities scheduled for the final trial visit should be performed at the time of discontinuation whenever possible. Any adverse events which are present at the time of discontinuation/withdrawal should be followed in accordance with the safety requirements outlined in Section 7.2. Subjects who a) attain a CR or b) complete 24 months of treatment with pembrolizumab may discontinue treatment with the option of restarting treatment if they meet the criteria specified in Section 7.1.6.4. After discontinuing treatment following assessment of CR, these subjects should return to the site for a Safety Follow-up Visit (described in Section 7.1.6.1) and then proceed to the Follow-Up Period of the study (described in Section 7.1.6.2).

7.1.4.2 Blinding/Unblinding

This is an open-label trial.

7.1.5 Visit Requirements

Visit requirements are outlined in Section 6.0 - Schedule of Assessments. Specific procedure-related details are provided above in Section 7.1 - Trial Procedures.

7.1.6 Follow-up Requirements

7.1.6.1 Safety Follow-up Visit

The mandatory Safety Follow-up Visit should be conducted approximately 30 days after treatment discontinuation or before the initiation of a new anti-cancer treatment, whichever comes first. All AEs that occur prior to the Safety Follow-up Visit should be recorded. Subjects with an AE of Grade > 1 will be followed until the resolution of the AE to Grade 0-1 or until the beginning of a new anti-neoplastic therapy, whichever occurs first. SAEs that occur within 90 days of the end of treatment or before initiation of a new anti-cancer treatment should also be followed and recorded. Subjects who are eligible for retreatment with pembrolizumab (as described in Section 7.1.6.4) may have up to two Safety Follow-up Visits, one after the Treatment Period and one after the Retreatment Phase.

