Anorexia	226	(13.0)	23	(1.3)	197	(11.3)	21	(1.2)
Hyperglycaemia	223	(12.8)	42	(2.4)	139	(8.0)	21	(1.2)
Leukopenia	211	(12.1)	112	(6.4)	170	(9.7)	75	(4.3)
Headache	210	(12.0)	10	(0.6)	88	(5.0)	6	(0.3)
Dizziness	207	(11.9)	14	(0.8)	108	(6.2)	8	(0.5)
Dysgeusia	203	(11.6)	2	(0.1)	186	(10.7)	2	(0.1)
Alopecia	188	(10.8)	11	(0.6)	139	(8.0)	8	(0.5)
Abdominal pain	184	(10.6)	22	(1.3)	95	(5.4)	6	(0.3)
Hypokalaemia	179	(10.3)	67	(3.8)	90	(5.2)	31	(1.8)
Back pain	177	(10.1)	24	(1.4)	19	(1.1)	2	(0.1)

Every patient is counted a single time for each applicable specific adverse event. A patient with multiple adverse events within a system organ class is counted a single time for that system organ class.

A system organ class or specific adverse event appears on this report only if its incidence in one or more of the columns is greater than or equal to the percent incidence specified in the report title, after rounding.

Only the highest reported grade of a given adverse event is counted for the individual patient.

Pembrolizumab:

AEs associated with pembrolizumab exposure, including coadministration with additional compounds, may represent an immunologic aetiology. These immune-related AEs (irAEs) may occur shortly after the first dose or several months after the last dose of pembrolizumab/combination treatment and may affect more than one body system simultaneously. Therefore, early recognition and initiation of treatment is critical to reduce complications. Based on existing clinical study data, most irAEs were reversible and could be managed with interruptions of pembrolizumab/combination treatment, administration of corticosteroids and/or other supportive care. For suspected irAEs, ensure adequate evaluation to confirm etiology or exclude other causes. Additional procedures or tests such as bronchoscopy, endoscopy, skin biopsy may be included as part of the evaluation. Dose modification and toxicity management guidelines for irAEs associated with pembrolizumab/combination treatment are provided in Table 3.

Attribution of Toxicity:

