The End of Treatment and Follow-up visit procedures are listed in Section 6 (Schedule of Assessments) and Section 7.1.6 (Follow-up Requirements). After the end of treatment, each subject will be followed for 30 days for adverse event monitoring (serious adverse events will be collected for 90 days after the end of treatment as described in Section 7.2). Subjects who discontinue for reasons other than progressive disease will have post-treatment follow-up for disease status until disease progression, initiating a non-study cancer treatment, withdrawing consent or becoming lost to follow-up. After documented disease progression, each subject will be followed by telephone for overall survival until death, withdrawal of consent, or the end of the study, whichever occurs first.

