Correlative Studies Blood Collection	x	x ⁸	x	x	x	x	x	x	x	x	x ¹⁰				

Footnotes:

¹ Procedures completed prior to consenting that are a part of a subject's standard of care may be used if they fall within the 28 day window to start treatment. Screening procedures completed 7 days of C1D1 do not need to be repeated.

² If the subject discontinues treatment due to disease progression, a phone call to the patient can serve as the Safety Follow-up Visit if the End of Treatment Visit was done. If a subject initiates a new anti-cancer therapy within 30 days after the treatment discontinuation, the 30 day Safety Follow-up Visit must occur before the first dose of the new therapy. Once new anti-cancer therapy has been initiated the subject will move into Survival Follow-up.

³ Applies to subjects who discontinue trial treatment for a reason other than disease progression. Subjects should be assessed per institutional guidelines by radiologic imaging to monitor disease status. Every effort should be made to collect information regarding disease status until the start of new anti-neoplastic therapy, disease progression, death, end of the study or if the subject begins retreatment with pembrolizumab.

⁴ Full physical exams may also be done by the investigator or qualified designee throughout participation in the trial as clinically indicated.

⁵ Only if clinically indicated and must be completed \leq 7 days prior to the first dose of study medication

⁶ It is recommended that after 1 year, imaging should be done every 6 months \pm 2 weeks; however, institutional guidelines and investigator discretion may vary.

⁷ Whenever possible, archival tissue from a tumor lesion will be obtained at screening. However, patients will be given the option to consent to a biopsy during the screening phase in case archival tissue cannot be retrieved and a second biopsy on Cycle 1 Day 14 (- 3 days). Missed tissue collection will not be considered a protocol deviation for the purposes of this study, as tissue collection is an exploratory objective for this study.

⁸ Run-in Phase, Cycle -2 Days 1 and 14

⁹ Laboratory tests for screening or entry into the Retreatment Phase should be performed within 10 days prior to the first dose of treatment. After Cycle 1, pre-dose laboratory procedures can be conducted up to 72 hours prior to dosing. Results must be reviewed by the investigator or qualified designee and found to be acceptable prior to each dose of trial treatment.

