7.1.6.3 Survival Follow-up

Once a subject experiences confirmed disease progression or starts a new anti-cancer therapy, the subject moves into the survival follow-up phase and will be monitored every 6 months (\pm 30 days) to assess for survival status until death, withdrawal of consent, or the end of the study, whichever occurs first.

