7.2.1.2 Serious Adverse Event (SAE)

A serious adverse event is any untoward medical occurrence resulting in one or more of the following:

- Results in death or ANY death occurring within 90 days of last dose of study drug (even if it is not felt to be drug related)
- Is life-threatening (defined as an event in which the patient was at risk of death at the time of the event; it does not refer to an event which hypothetically might have caused death if it were more severe)
- Requires inpatient hospitalization or prolongation of existing hospitalization

NOTE: Hospitalizations that are not considered SAEs are:

- Hospitalization planned prior to first administration of study drug
- Hospitalization for elective treatment of a pre-existing condition unrelated to the study medication
- Results in persistent or significant disability/incapacity
- Is a congenital anomaly or birth defect
- Is an important medical event (defined as a medical event(s) that may not be immediately life-threatening or result in death or hospitalization but, based upon appropriate medical and scientific judgment, may jeopardize the patient or may require intervention (e.g., medical, surgical) to prevent one of the other serious outcomes listed in the definition above). Examples of such events include, but are not limited to, intensive treatment in an emergency room or at home for allergic bronchospasm; blood dyscrasias or convulsions not resulting in hospitalization; or the development of drug dependency or drug abuse.
- Pregnancy

- Pregnancy of a patient or of the female partner of a male patient during the study or within 120 days after the last dose of study drug should be reported via an SAE report. Should pregnancy occur in a female participant during the treatment period, study drug should be discontinued and Merck notified immediately. Should a pregnancy occur in a female companion of a male participant during the treatment period, the male participant can continue treatment and Merck notified immediately. Any such pregnancy is to be followed until final outcome. Evaluating Adverse Events
- In addition to the above criteria, AEs meeting either of the below criteria, although not serious per ICH definition, are reportable to Merck in the same time frame as SAEs to meet certain local requirements. Therefore, these events are considered serious by Merck for collection purposes.
 - Is a new cancer (that is not a condition of the study)

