7.2.4 Events of Clinical Interest

Selected non-serious and serious adverse events are also known as Events of Clinical Interest (ECI) and must be recorded as such on the Adverse Event case report forms and reported as described in sections 5.2.1.6 and 10.5. Events of Clinical Interest for this trial include:

1. An overdose of pembrolizumab, as defined in Section 7.2.2 - Definition of an Overdose, that is not associated with clinical symptoms or abnormal laboratory results.

2. An elevated AST or ALT lab value that is greater than or equal to 3X the upper limit of normal and an elevated total bilirubin lab value that is greater than or equal to 2X the upper limit of normal and, at the same time, an alkaline phosphatase lab value that is less than 2X the upper limit of normal, as determined by way of protocol-specified laboratory testing or unscheduled laboratory testing.*

*Note: These criteria are based upon available regulatory guidance documents. The purpose of the criteria is to specify a threshold of abnormal hepatic tests that may require an additional evaluation for an underlying etiology. The trial site guidance for assessment and follow up of these criteria can be found in the Investigator Trial File Binder (or equivalent).

3. Additional adverse events:

A separate guidance document has been provided entitled “Event of Clinical Interest Guidance Document” (previously entitled, “Event of Clinical Interest and Immune-Related Adverse Event Guidance Document”). This document can be found in Appendix 14.5 and provides guidance regarding identification, evaluation and management of ECIs and irAEs.

ECIs (both non-serious and serious adverse events) identified in this guidance document from the date of first dose through 90 days following cessation of treatment, or 30 days after the initiation of a new anticancer therapy, whichever is earlier, need to be reported as described in sections 5.2.1.6 and 10.5 regardless of attribution to study treatment, consistent with standard SAE reporting guidelines.

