7.3 Participating Site Reporting Responsibilities

7.3.1 Reporting SAEs, ECIs and Pregnancy to the Coordinating Center (IU Simon Comprehensive Cancer Center)

Any serious adverse event, unanticipated problem, event of clinical interest or pregnancy occurring from the first dose of vorinostat to within 90 days from the last dose of study drug must be reported to the IU Simon Comprehensive Cancer Center within 24 hours of notification or discovery of the incident, using the MedWatch Form 3500A (Mandatory Reporting). This form must be accompanied by a cover letter which: identifies the event, is signed by the local principal investigator or treating physician, includes the applicable study number and title, and contains the following:

- Site assessment of the event attribution to investigational treatment or study procedure
- Site assessment of event expectedness (expected vs. unexpected)

- Assessment of whether or not the research places subjects at a greater risk of harm than was previously known or recognized
- Assessment of the event's affect on the risk to benefit ratio
- Statement as to whether the informed consent statement should reflect changes in the potential risks involved
- Statement as to whether the event has been reported previously, and if so, whether the frequency is considered unusually high

Send to: IUSCC Clinical Trials Office
 ATTN: Multicenter coordinator/ IUSCC-0551
 Preferred E-mail: [contact]
 Backup [contact]

All SAEs must also be entered into OnCore for **monthly review** by the DSMC Coordinator. The Multicenter Network Administrator, or designee, will distribute all reports meeting expedited reporting criteria to all participating sites, the FDA and to Merck. Copies of all serious adverse event reports will be kept on file in the IU Simon Comprehensive Cancer Center Clinical Trials Office.

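### SAEs and ECIs are due to day 90, but patients who progress or start new therapy have no scheduled safety contact after about day 30, and the sections differ on whether new therapy ends collection

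*Combined protocol and SAP*

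**What the plan says.** **Collection windows**

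- Section 5.6: "serious adverse events will be collected for 90 days after the end of treatment as described in Section 7.2". Section 7.2 itself gives a 90-day limit only for deaths and for ECIs, so the cross-reference does not settle the general SAE rule.
- Section 7.1.6.1: "SAEs that occur within 90 days of the end of treatment or before initiation of a new anti-cancer treatment should also be followed and recorded".
- Section 7.2.4, for ECIs: from first dose "through 90 days following cessation of treatment, or 30 days after the initiation of a new anticancer therapy, whichever is earlier".
- Section 7.3.1, for any SAE, unanticipated problem, ECI or pregnancy "occurring from the first dose of vorinostat to within 90 days from the last dose of study drug must be reported" to the coordinating center.
- Section 7.2.1.2 counts as serious "ANY death occurring within 90 days of last dose of study drug", whether or not it is thought drug-related.

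**Planned contacts**

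- The Safety Follow-up Visit is at day 30 ± 3 in Section 6.0, and is brought forward if new therapy starts sooner. After progression a phone call can serve, provided the End of Treatment Visit was done (footnote 2).
- The same footnote adds: "Once new anti-cancer therapy has been initiated the subject will move into Survival Follow-up". Under Section 7.1.6.3, patients with confirmed progression or new therapy "will be monitored every 6 months" (± 30 days) for survival status.
- Patients who stop for another reason are imaged according to institutional practice (Section 7.1.6.2), or every 9 weeks in Year 1 (Section 14.3.4). The stated purpose is disease status.

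**Risk period.** Section 5.2.1.6 says immune-related events "may occur shortly after the first dose or several months after the last dose of pembrolizumab/combination treatment".

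**The concern.** The window for serious and immune-related events is three times as long as the period that ends with the last mandated safety visit. The protocol itself says that such events can arise months after dosing. For patients who progress or move to another therapy, nothing prompts a site to ask about days 31 to 90. What reaches the database from that period depends on what the site happens to learn.

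A site that does learn of an event then finds sections that differ on whether a new therapy closes the window. In a multicenter trial the same event could be recorded under one section and left out under another.

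The overall safety profile is a secondary objective. Section 8.10 reports simple proportions of the safety population and states no collection window, so the analysis plan does not resolve the difference.

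**Working it through.** No sample size, power or error rate is involved, and the plan states no figure to reproduce. The check is date arithmetic on the stated windows, followed by a comparison of the sections.

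**1. Days after the last mandated safety visit.** Days in the window after the visit = 90 − visit day, with the visit at 30 ± 3 (Section 6.0).

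| Visit day | Days left | Share of 90 |
|---|---|---|
| 27 | 63 | 70% |
| 30 | 60 | 67% |
| 33 | 57 | 63% |

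If new therapy starts before day 30, the visit moves earlier and the remainder grows.

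**2. Next contact.** After progression or new therapy it is at 6 months ± 30 days. Taking 6 months as 180 days from end of treatment (an assumption, since the origin is not stated), this is days 150 to 210, wholly beyond day 90. Patients who stop for other reasons are due a scan within 63 days of the last one under Section 14.3.4, so normally inside the window.

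**3. End of collection if new therapy starts on day s.** All windows are counted here from a common day zero.

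- Sections 5.6 (SAEs) and 7.3.1 (SAEs and ECIs): 90
- Section 7.2.4 (ECIs): min(90, s + 30)
- Section 7.1.6.1 (SAEs): min(90, s) if new therapy is a cut-off; 90 if the wording is inclusive

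| s | 5.6 / 7.3.1 | 7.2.4 | 7.1.6.1, cut-off | 7.1.6.1, inclusive |
|---|---|---|---|---|
| 20 | 90 | 50 | 20 | 90 |
| 35 | 90 | 65 | 35 | 90 |
| 45 | 90 | 75 | 45 | 90 |
| 60 | 90 | 90 | 60 | 90 |

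The firm conflict is 7.2.4 against 7.3.1 for ECIs, whenever s is below 60. With s = 35, an ECI on day 75 falls after day 65 and outside 7.2.4, but is reportable under 7.3.1. For SAEs, 7.1.6.1 conflicts with 5.6 and 7.3.1 only on the cut-off reading.

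**4. Day zero.** It is end of treatment in 5.6 and 7.1.6.1, cessation of treatment in 7.2.4, and last dose in 7.2.1.2 and 7.3.1. These need not be the same date.

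**5. Events still open.** Section 7.1.6.1 follows an AE above Grade 1 until Grade 0–1 or new therapy, whichever is first. The text under 7.3.2/7.3.3 follows all reported events to resolution, stabilization, another explanation or loss to follow-up, and does not stop at new therapy.

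**6. Scale, on assumed inputs only.** Expected patients missed = N × q × (1 − a), where q is the share of patients with an SAE or ECI in days 31–90 and a is the share of those captured. Take N = 57, q from 5% to 15%, and a from 50% to 75%.

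- Low: 57 × 0.05 × 0.25 = 0.7
- High: 57 × 0.15 × 0.50 = 4.3
- With full capture: 0

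**The case against.** A reader might infer that late immune toxicity is under-counted and that rates are biased low by differing amounts across sites. The documents do not show this. Section 7.3.1 obliges sites to report, within 24 hours of notification or discovery, any SAE or ECI to day 90. Section 5.3.1 asks for concomitant medication beyond day 30 to be recorded for SAEs and ECIs, and the text under 7.3.2/7.3.3 requires proactive follow-up of events already reported. A death found at the first survival contact is late, not lost. This stands: the supported statement is possible under-ascertainment.

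It is also tempting to say that every patient goes unseen from day 30 to month 6. That holds only after progression or new therapy, since the others have imaging follow-up. Those visits are not described as safety assessments. The alignment of the adverse-event row in the Section 6.0 table is unclear in the text available, so nothing is rested on it; on neither possible alignment does a mark reach Survival Follow-up.

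Nor does Section 7.1.6.1 clearly stop SAE collection on the day new therapy starts. Two neighboring sentences say that the earlier date governs, but the SAE sentence does not, and read inclusively it agrees with 5.6 and 7.3.1. That is an ambiguity, not a demonstrated exclusion. Likewise, an SAE on day 75 after new therapy on day 35 is collectable under 5.6 as well as 7.3.1, so the clean contradiction concerns ECIs.

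Finally, dose-limiting toxicity monitoring uses the first 21 days and is unaffected, and no statistical comparisons are planned.

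**Conclusion.** The point holds in limited form. For patients who progress or start new therapy, 57 to 63 of the 90 days (63% to 70%) follow the last mandated safety visit, and more if that visit is brought forward. No section schedules a safety enquiry again before the window closes. For patients who stop for other reasons the gap is one of purpose: they are imaged, but the protocol does not say they are asked about adverse events.

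There are at most three new-therapy rules. The 7.2.4 and 7.3.1 rules for ECIs contradict each other, and 7.1.6.1 needs clarifying against 5.6 and 7.3.1 for SAEs. The AE follow-up rules in 7.1.6.1 and 7.3.2/7.3.3 also disagree, and day zero is not uniform.

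Late SAEs and ECIs may be under-ascertained, by an amount the documents do not allow anyone to estimate. The range of 0.7 to 4.3 patients rests wholly on assumed rates, and full capture would make it zero. This should be corrected because it bears on a secondary objective and is cheap to put right.

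**What to change.** - State one SAE/ECI window, with one start date and one new-therapy rule, in Sections 5.6, 7.1.6.1, 7.2.4 and 7.3.1. Ninety days from the last dose of study drug, whether or not new therapy has begun, already matches 7.3.1 and the death criterion in 7.2.1.2. Other rules would also be consistent, and the need is for a single one.
- State the same window in Section 8.10. Tabulate events that begin after new therapy separately, using the post-study therapy data already collected under Sections 6.0 and 7.1.1.5.3.
- Add to Section 6.0 one telephone safety contact at the end of the window (about day 90), asking about SAEs, ECIs and survival.
- Reconcile the follow-up of open AEs in 7.1.6.1 with 7.3.2/7.3.3.

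The cost is wording in these sections and one call for each of 51 to 57 patients, with no added procedure. The downside is that some events recorded after new therapy will be confounded by it. The separate tabulation makes those events visible but does not remove the confounding.
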